3.5.4 Pharmacokinetic Set

The Pharmacokinetic Set (PKS) is a subset of the FAS, consisting of those study participants who had no important protocol deviations affecting the PK parameters and had a sufficient number of samples available to determine at least one PK parameter. All PK analyses will be performed using the PKS.

3.6 Treatment assignment

Tables will be presented by cohort (Cohort A: Healthy Study Participants and Cohort B: Participants with Moderate Hepatic Impairment) and overall. Listings will be presented by study participants, cohort and study period as described in Section 3.2.2. PK summaries will be presented by treatment period (Single Dose and Multiple Dose), cohort and analyte (PSL and two of its metabolites).

A detailed schematic diagram of the study is provided in Table 3.1

Table 3–1: Padsevonil administration

Cohort A (Healthy Study Participants) and Cohort B (Child-Pugh Hepatic Insufficiency Classification of Moderate) (n=approximately 12 per cohort)											
	Single Dose			Multiple Dose							EOS/ETV
	Treatment Period	Washout Period		Treatment Period					Washout Period		
Day	1	2 to 5	6 to 7	8	9	10	11	12 (AM)	12 (PM)	13 to 17	18
PSL Dose (mg)	100 AM only			100 BID	100 BID	100 BID	100 BID	100 AM only			
Blood Sample	PK	PK (each day)		PK	PK	PK	PK	PK	PK	PK (until Day 17)	
Urine Sample	PK	PK (each day)						PK			

BID=twice daily; EOS=End of Study; ETV=Early Termination Visit; PK=pharmacokinetic; PSL=padsevonil

3.7 Center pooling strategy

The data will come from one center. The statistical analyses will not be performed by center.

3.8 Coding dictionaries

Adverse events and medical history will be coded using the latest available version of the Medical Dictionary for Regulatory Activities (MedDRA®). Medications will be coded according to the latest version of the World Health Organization Drug Dictionary (WHODD) (Version SEP/2017). Medical procedures will not be coded.

3.9 Changes to protocol-defined analyses

- Changes in the name of analysis datasets (section 9.1 of the protocol):
 - The analysis set “Enrolled set” will be renamed as “All Study Participants” in the SAP and will correspond to all study participants who sign the informed consent form.
 - The analysis set “Pharmacokinetic Per Protocol Set (PK-PPS)” will be renamed as “Pharmacokinetic Set (PK Set)” in the SAP and will still correspond to the definition of PK-PPS.
- Inclusion of a new analysis set: the Safety Set: The Safety Set was included in the SAP for the analysis of the safety parameters. The definition is given in section 3.5.1 of the SAP.
- Definition of Baseline for 12 lead ECG: The protocol states that the baseline ECG value will be the time-matched baseline day of each treatment period, when applicable. In the SAP, the ECG baseline value is defined as the mean of the last three predose measurements. If less than three predose replicates are available, the mean of the available predose replicates will be taken as the baseline.
- The data for the other endpoint “Bound and unbound plasma concentration of PSL in 2 samples” will not be available at the time of CSR/ Database lock and thus this will not be reported in the TFLs delivery. This will be addressed in a different report.
- Regarding the analysis of the vital signs, in the protocol, it is mentioned that frequency table of values outside the normal ranges will be produced by cohort and time points. This table will not be produced and is not mentioned in this SAP.
- For the two metabolites, the urine PK parameter, f_{met} , has been specified.

4 STATISTICAL/ANALYTICAL ISSUES

4.1 Adjustments for covariates

Not applicable.

4.2 Handling of dropouts or missing data

In general, there will be no imputation of missing data unless otherwise stated below.

Missing data will be handled as described in the sections below for safety laboratory and PK results. No other imputations will be performed.

4.2.1 Pharmacokinetics

The 95% CI lower and 95% CI upper should be left blank if the standard deviation (or equivalently, the geometric CV) is 0. Measurements of PK concentrations that are below the limit of quantification (BLQ) and which are occurring prior to t_{max} will be imputed with half of the lower limit of quantification (LLOQ/2), except for embedded BLQ values (between two measurable data points) which will be treated as missing, for the purpose of calculating the geometric mean and its 95% CI, the geometric CV, the arithmetic mean and standard deviation for summaries and figures. Post- t_{max} , BLQ values will be treated as missing. Descriptive statistics of concentrations will be calculated if at least 2/3rd of the individual data points are quantifiable (\geq LLOQ).

For all individual PK concentration figures, any concentrations that are BLQ will be regarded as missing, with the exception of predose BLQ measurements which will be imputed with zero (to capture lag-time) for linear scale plots.

The following rules will apply for PK data listings:

- Values below the LLOQ will be reported as “(BLQ)” in the listings

The following rules will apply for PK summaries

- Descriptive statistics of plasma concentrations will be calculated if more than 2/3rd of individual data points are quantifiable (\geq LLOQ) at the given time-point. However, if $n < 3$, then only n , minimum and maximum will be presented, and the median will also be presented if $n=3$. The other descriptive statistics will be left blank.
- For t_{max} , $t_{1/2}$, and $t_{1/2ss}$ only N , median, minimum and maximum will be displayed into the summary statistics,
- For plasma concentration summaries, all BLQ values will be replaced by “LLOQ/2” and missing values will be excluded.
- When the mean value includes one or more replaced BLQ values then a footnote will be included to say “contains one or more BLQ value replaced by half the LLOQ value”.
- For the individual figures, any concentrations that are BLQ will be regarded as missing, with the exception of predose BLQ measurements which will be imputed with zero for linear scale plots.
- If no participants have data, only $n=0$ will be presented. The other descriptive statistics will be left blank.
- The geometric CV will be calculated using the following formula where SD_{log} is the standard deviation from the log-transformed data:

$$\text{Geometric CV (\%)} = \text{sqrt}[(\exp(SD_{log}^2) - 1)] \times 100$$

The PK analysis will be performed in accordance to the Guideline on performing NCA analysis dated 08 Nov 2017, and BLQ values will be treated as stated in this document for the NCA analysis.

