### 4.2 Scientific rationale for study design

In healthy volunteers without hepatic impairment, the concentration-time profiles of both PSL and [REDACTED] demonstrated a biphasic disposition with a terminal elimination half-life ( $t_{1/2}$ ) of approximately 6 hours for the parent, and 10 to 14 hours for the metabolite, which were independent of dose. However, steady state was achieved after 2 to 3 days of treatment for both moieties, and the accumulation ratio for the parent was approximately 1.7 (range 1.59 to 2.11), which was greater than predicted by the single dose PK (N01386).

As PSL is cleared hepatically, exposure to drug in hepatically impaired participants could increase primarily due to a reduction in PSL clearance, among other factors. This can be illustrated by an increase in  $t_{1/2}$ , a prolonged washout time, and an increased time to reach steady state with multiple dosing. To facilitate the design of this study, a doubling of  $t_{1/2}$  and time to steady state has been assumed in hepatically impaired participants. Therefore, the Washout Period required to capture the  $t_{1/2}$  of the [REDACTED] has been calculated to be 5 to 6 days (assumes a  $t_{1/2}$  of 28 hours) and the time to steady state has been calculated to be 4 to 6 days.

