### **9.2 General statistical considerations**

Statistical evaluation will be performed by the Sponsor or designee and supervised by the Early Development Statistics Department of UCB. All statistical analyses will be performed using SAS® Version 9.4 or later (SAS Institute, Cary, NC, USA).

For continuous variables, summary statistics will include number of study participants, mean, median, standard deviation, minimum, and maximum (geometric mean and geometric coefficient of variation [CV] for plasma concentrations and PK parameters). Categorical endpoints will be summarized using number of study participants, frequency, and percentages. Missing data will not be imputed. Individual plasma concentration and PK parameters will be presented using three significant digits.

If not otherwise stated, Baseline will be the last assessment prior to dosing. Measurement of specific Baseline values will be described in the SAP.

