## 9.3 Planned safety and other analyses

### 9.3.1 Pharmacokinetic analyses

Pharmacokinetic parameters will be determined by non-compartmental analysis with Pharsight Phoenix® WinNonlin® v6.3 (or higher) software using the PK-PPS.

Pharmacokinetic parameters of PSL and its major metabolites (██████████) will be computed using the actual blood sampling time points.

The plasma concentration-time profiles, urine amounts, and PK parameters of PSL and its metabolites will be summarized by cohort (group), treatment period, and day using descriptive statistics (number of available observations, arithmetic mean, standard deviation, geometric mean, and CV of the geometric mean, median, minimum, and maximum).

Individual plasma PSL and metabolites concentration-time profiles will be displayed graphically on a linear-linear scale and semi-logarithmic scale (including spaghetti plots). Geometric mean plasma concentrations-time curves, including 95% confidence intervals (CIs), will be displayed by cohort.

For the Single- and Multiple-Dose Treatment Periods, PK parameters (including AUC, AUCτ, Cmax,ss, and Cmax) of PSL will be compared between the 2 cohorts (healthy and hepatically impaired participants) using analysis of variance (ANOVA) as follows: point estimates for the ratio of geometric means between healthy and hepatically impaired participants and the respective 2-sided 90% CIs will be computed using the least squares means and the root mean squares of error from the ANOVA of the log-transformed data with subsequent exponential transformation. Interstudy participant variability of PK parameters will be derived from these analyses.

Graphical representation of the data (eg, Scatter plots) and/or linear regression analysis of the primary PK parameters (AUC and Cmax) of PSL and metabolites against the Child-Pugh parameters of total bilirubin, albumin, and prothrombin time will be also provided, if feasible.

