3 DATA ANALYSIS CONSIDERATIONS

3.1 General presentation of summaries and analyses

Statistical evaluation will be performed by ICON PLC and supervised by UCB. The datasets will follow the UCB analysis data model (ADaM) data specifications. All statistical analyses will be performed using SAS[®] Version 9.4 or later (SAS Institute, Cary, NC, USA).

Pharmacokinetic parameters will be determined by non-compartmental analysis (NCA) with Pharsight Phoenix WinNonlin[®] v6.3 or higher (Certara L.P., Princeton, NJ, NCA) for PK parameter estimation using actual doses administered and the actual sampling times relative to time of dose administration.

Categorical endpoints will be summarized using number of study participants (n), frequency, and percentages. Missing data will not be imputed. Individual plasma and urine concentration and PK parameters will be presented using 3 significant digits.

When reporting relative frequencies or other percentage values, the following rules apply:

- For values where all study participants fulfill certain criteria, the percentage value will be displayed as 100
- For values where the absolute frequency is zero, there will be no percentage displayed
- All other percentage displays will use 1 decimal place

Percentages displayed based on continuous data (e.g. percentage changes from baseline) will be displayed to 1 decimal place. Unless otherwise stated, the denominator for the percentages will be based on the number of participants in the respective analysis set.

Continuous variables will be summarized by visit and time point (where applicable) including number of study participants (n), mean, median, standard deviation (sd), minimum and maximum. Geometric coefficient of variation (geoCV), geometric mean and 95% confidence interval (CI) for the geometric mean will also be presented in the descriptive statistics for the plasma concentration and PK parameters for PSL and two of its metabolites (██████████) and ██████████. In all outputs, the confidence limits will be restricted to the possible values that the variable can take.

When reporting descriptive statistics, the following rules will apply in general except for PK concentration data (plasma and urine PK) of PSL and two of its metabolites ([REDACTED] and [REDACTED])::

- n will be an integer

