9.3 Analysis of other pharmacokinetic variables

The other PK parameters for PSL metabolites ([REDACTED] and [REDACTED]) include:

- Single Dose Period: AUC_{0-t} , AUC , C_{max} , t_{max} , $t_{1/2}$, AUC_{0-12} , MR_{AUC} , $MR_{C_{max}}$
- Multiple Dose Period: $C_{max,ss}$, AUC_{τ} , t_{max} , $t_{1/2,ss}$, C_{trough} , $MR_{AUC_{\tau}}$, $MR_{C_{max,ss}}$

C_{max} and $C_{max,ss}$ will be determined from the observed concentration and time data. AUC_{τ} , AUC and AUC_{0-t} will be computed using the linear up/log down trapezoidal rule.

The other PK parameters for PSL include:

- Single Dose Period: CL/F , t_{max} , $t_{1/2}$, AUC_{0-12}
- Multiple Dose Period: CL_{SS}/F , t_{max} , $t_{1/2,ss}$, C_{trough} ,

- Bound and unbound plasma concentration of PSL will be analyzed in two samples. Results of analysis of bound and unbound plasma concentration of PSL will be presented in a different report, after final analysis will be provided.

CL/F and CL_{SS}/F will be determined from the observed concentration and time data.

The other PK parameters in urine of PSL and two of its metabolites ([REDACTED] and [REDACTED]) are: Ae, CL_R, fe (PSL only), MR_{Ae} and fe_{met} (metabolites only).

The other PK parameters and the amount of urinary excretion of PSL and its metabolites will be summarized by treatment period, cohort and nominal sampling times using descriptive statistics (number of available observations [n], arithmetic mean, median, standard deviation, minimum, maximum, geometric mean, geometric CV and 95% CI for the geometric mean [assuming lognormally distributed data]). Values below the LLOQ will be reported with a clear sign (flag variable in the dataset) indicating that they were below the LLOQ. t_{max}, t_{1/2}, and t_{1/2SS} will only display the number of available observations [n], median, minimum, and maximum.

The point estimate and the 95% CI for the median differences for t_{max} between the 2 cohorts (healthy participants and participants with moderate hepatic impairment) will be computed according to the Hodges-Lehmann method.

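### SAP 4.2.1 and 9.3 cut half-life to a count, median and range, against protocol 9.2 and 9.3.1 and without a declaration in SAP 3.9, so the tables give half-life no measure of precision

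*SAP*

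**What the plan says.** SAP 4.2.1 groups t1/2 and t1/2,ss with tmax and states that "only N , median, minimum and maximum will be displayed into the summary statistics". SAP 9.3 first gives the other PK parameters the full set of statistics, then exempts the same three, which "will only display the number of available observations [n], median, minimum, and maximum".

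The protocol makes no such exemption. Section 9.2 provides "geometric mean and geometric coefficient of variation [CV] for plasma concentrations and PK parameters". Section 9.3.1 states that "PK parameters of PSL and its metabolites will be summarized by cohort (group), treatment period, and day using descriptive statistics" and lists "arithmetic mean, standard deviation, geometric mean, and CV of the geometric mean, median, minimum, and maximum" among them. SAP 3.1 sets a general rule that, besides the geometric CV, the "geometric mean and 95% confidence interval (CI) for the geometric mean will also be presented in the descriptive statistics", again with no exception for half-life.

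SAP 3.9 lists the changes to protocol-defined analyses: renamed analysis sets, a new Safety Set, the ECG baseline, deferred protein-binding results, a dropped vital-signs table and a specified metabolite urine fraction. The half-life summary is not among them.

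For cohort comparisons, SAP 9.1 applies the log-scale ANOVA (ratio with 90% CI) to the primary parameters only. SAP 9.3 gives tmax a Hodges-Lehmann difference with a 95% CI. Half-life gets neither.

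Protocol 4.2 says that a doubling of t1/2 "and time to steady state has been assumed in hepatically impaired participants", and derives the washout and the time to steady state from it.

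**The concern.** The SAP removes statistics that the protocol planned for a listed endpoint, gives no reason, and omits the removal from the section meant to record such changes.

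A count, median and range suit tmax, which is read off the sampling times and so clusters on the schedule. Half-life is a continuous estimate from the terminal slope, and the protocol treated it like the other PK parameters.

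The protocol expects reduced clearance in hepatic impairment to show as a longer half-life, and it uses an assumed doubling to set two features of the design. A reader of the report will want to know how well that assumption held. From the planned tables, that reader would see two medians and two ranges, with nothing to show how precisely either cohort's half-life, or the ratio between them, was estimated.

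**Working it through.** **1. The plan's own figures.**
- *Power* (protocol 9.8, SAP 2.3): 12 per group, ratio 2.000, CV 0.40 for AUCss, one-sided 0.05. Log-scale SD = √ln(1 + 0.40²) = 0.385; difference = ln 2 = 0.693. A noncentral t with 22 df gives power 0.996, consistent with the stated figure of more than 90%. No half-life input enters.
- *Washout* (protocol 4.2): the metabolite half-life in healthy volunteers is 10 to 14 h, and 2 × 14 = 28 h, the figure used. Assuming that washout means about five half-lives (the multiple is not stated), 5 × 28 = 140 h = 5.8 days, within the stated 5 to 6 days.
- *Time to steady state* (protocol 4.2): 2 × (2 to 3 days) = 4 to 6 days, as stated.

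So the doubling sets the washout and the time to steady state, and does not enter the sample size.

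**2. Statistics for t1/2 and t1/2,ss, by source.**

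| Source | Median, range | Geometric mean, geometric CV | 95% CI of geometric mean |
|---|---|---|---|
| Protocol 9.2, 9.3.1 | yes | yes | not stated for parameters |
| SAP 3.1 (general rule) | yes | yes | yes |
| SAP 4.2.1, 9.3 (specific rule) | yes | no | no |

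The specific rule also drops the arithmetic mean and SD.

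**3. What an estimate would deliver.** The documents give no CV for half-life, so 20% to 60% is an assumed range; 40% is the protocol's figure for AUCss. Also assumed are a log-normal half-life, 12 estimable values per cohort and a true impaired/healthy ratio of 2.0.

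- SD_log = √ln(1 + CV²)
- 90% CI for the ratio: 2.0 ×/÷ exp[t(0.95; 22) × SD_log × √(2/12)], with t = 1.717
- 95% CI for one cohort's geometric mean: ×/÷ exp[t(0.975; 11) × SD_log / √12], with t = 2.201

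At CV 40%: 1.717 × 0.385 × 0.408 = 0.270 and exp(0.270) = 1.31, so the interval is 2.0/1.31 to 2.0 × 1.31, or 1.53 to 2.62.

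| Assumed CV | 90% CI around ratio 2.0 | 95% CI factor, one cohort |
|---|---|---|
| 20% | 1.74 to 2.30 | 1.13 |
| 40% | 1.53 to 2.62 | 1.28 |
| 60% | 1.36 to 2.95 | 1.42 |

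Even at 60% the ratio's interval excludes 1, so it would be informative with 12 per cohort. The planned tables contain neither interval.

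**The case against.** The other side has good points.

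- *The operative rule is clear.* SAP 4.2.1 and 9.3 agree, a specific rule overrides the general one in SAP 3.1, and SAP 1 lets stated SAP text replace the protocol. This stands: a programmer knows what to produce. What remains is an unexplained departure that SAP 3.9 should have recorded.
- *A median is robust when a terminal phase is poorly defined.* True, but the protocol's set already includes the median and range. Restoring the geometric mean and CV removes nothing.
- *Half-life is an Other endpoint and the ANOVA follows the endpoint hierarchy.* This stands. A reader might infer that the SAP removed a planned cohort ratio. The documents do not support that: the ratio is absent because SAP 9.1 limits the ANOVA to primary parameters, and the protocol's open-ended list of compared parameters never names half-life. Nor did the protocol promise a CI for parameter summaries; its 95% CIs belong to the concentration curves. The CI comes from SAP 3.1.
- *The assumption can be checked in other ways.* Largely right. SAP 3.1 requires listings of all derived data, so a reader could compute a ratio by hand. Cohort medians are reported. Predose samples on Days 8 to 12 show carry-over and the approach to a plateau. It would be wrong to say that the doubling cannot be checked, or that the whole design rests on it.
- *Half-life does not identify mechanism.* A reader might infer that it separates greater absorption from slower elimination. It depends on volume as well as clearance, and protocol 2.1 expects changes in absorption, protein binding and distribution. That inference is too strong.

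**Conclusion.** The point holds as a modest one. The SAP drops the protocol-planned geometric mean and geometric CV for t1/2 and t1/2,ss, drops the 95% CI that its own general rule provides, and does not declare this in SAP 3.9. The summary tables therefore show no precision for the parameter whose assumed doubling sets the washout and the time to steady state, and no cohort contrast for it, while tmax gets one with a 95% CI.

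Sample size, power and the primary analyses are unaffected. What is lost is an estimate with stated precision in the report. The expected 90% CI around a true ratio of 2.0 runs from 1.74 to 2.30 (CV 20%), through 1.53 to 2.62 (CV 40%), to 1.36 to 2.95 (CV 60%). These figures rest on an assumed CV, log-normality and 12 estimable half-lives per cohort; fewer would widen them.

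**What to change.** 1. In SAP 4.2.1 and 9.3, limit the short summary to tmax.
2. Summarise t1/2 and t1/2,ss with the geometric mean and geometric CV (protocol 9.2 and 9.3.1) and a 95% CI for the geometric mean (SAP 3.1), keeping the median and range and the existing small-n rules.
3. As an exploratory addition, not a restoration, report the impaired/healthy geometric mean ratio with 90% CI for t1/2 and t1/2,ss. Do this for PSL and for the metabolite whose assumed 28 h half-life sets the washout, since a PSL ratio alone would not address the washout assumption.

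If the sponsor prefers the short summary for half-life, the minimum is to declare and justify it in SAP 3.9 and add the exception to SAP 3.1.

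The cost is SAP wording and a few table rows from models already programmed, with no new data. Under SAP 1, a change before database lock needs a SAP amendment; an analysis added later would be described, with its rationale, in the study report.

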4.2.2 Safety laboratory data

The rules for handling values that are BLQ or above the limit of quantification (ALQ) in the safety laboratory data will be the same as those described for PK data in [Section 4.2.1](#).

4.2.3 Electrocardiogram data

For the 12-lead ECG data, all calculations of changes from Baseline and descriptive statistics will be based on the mean of the triplicate assessments at each time point. In the event that there are not 3 available measurements at a given time point, the mean will be calculated based on the number of measurements for which data are provided.

